## 8 Safety and Adverse Events

Blood will be collected at regular intervals to assess electrolytes level, kidney function, coagulation factor, and measure of base. Urine will also be collected at regular intervals to assess calcium and protein levels. Routine urinalysis will also be performed to monitor for any significant changes in body fluids as a result of acetazolamide function. Monitoring for thrombocytopenia, electrolyte disturbances, and metabolic acidosis should be completed within 4 weeks of a dose increase. If significant changes occur in blood or urine tests, risk will be re-evaluated by the principal investigator to determine if acetazolamide should be continued as per below. The AE reporting period will encompass visits 0 to 9 of the study. If a subject withdraws early, we will attempt to assess AEs up to 91 weeks after enrollment through review of medical records.

## 8.1 Definitions

### Unanticipated Problems Involving Risk to Subjects or Others (UPIRTSO)

Any unanticipated problem or adverse event that meets the following three criteria:

- Serious: Serious problems or events that results in significant harm, (which may be physical, psychological, financial, social, economic, or legal) or increased risk for the subject or others (including individuals who are not research subjects). These include: (1) death; (2) life threatening adverse experience; (3) hospitalization - inpatient, new, or prolonged; (4) disability/incapacity - persistent or significant; (5) birth defect/anomaly; (6) breach of confidentiality and (7) other problems, events, or new information (i.e. publications, DSMB reports, interim findings, product labeling change) that in the opinion of the local investigator may adversely affect the rights, safety, or welfare of the subjects or others, or substantially compromise the research data, **AND**
- Unanticipated: (i.e. unexpected) problems or events are those that are not already described as potential risks in the protocol, consent document, not listed in the acetazolamide package insert, or not part of an underlying disease. A problem or event is "unanticipated" when it was unforeseeable at the time of its occurrence. A problem or event is "unanticipated" when it occurs at an increased frequency or at an increased severity than expected, **AND**
- Related: A problem or event is "related" if it is possibly related to the research procedures.

### Adverse Event

An untoward or undesirable experience associated with the use of a medical product (i.e. drug, device, biologic) or placebo in a patient or research subject. AEs may also be problems/events that in the opinion of the investigator may have adversely affected the rights, safety, or welfare of the subjects or others, or substantially compromised the research data.

### Serious Adverse Event

Adverse events are classified as serious or non-serious. Serious problems/events can be well defined and include;

- death
- life threatening adverse experience
- hospitalization
- inpatient, new, or prolonged; disability/incapacity
- persistent or significant disability or incapacity
- birth defect/anomaly

All adverse events that do not meet any of the criteria for serious, should be regarded as **non-serious adverse events**.

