## 1.5 Risks and Benefits

### Risks

In general, acetazolamide is considered a safe drug. Per the package insert, severe adverse reactions that have been reported with administration of acetazolamide include seizures, muscle paralysis, hepatic necrosis, hepatic failure, hepatic encephalopathy, toxic epidermal necrosis, agranulocytosis, anaphylaxis, aplastic anemia, hemolytic anemia, Stevens-Johnson syndrome, pancytopenia, acute generalized exanthematous pustulosis, renal failure, and renal tubular obstruction. The incidence of each reaction is unknown. It is likely that individuals who have significant baseline allergy to acetazolamide and other components, hepatic dysfunction, blood dyscrasias, and/or renal dysfunction would be at higher risk for these severe reactions. Thus we are assessing for hepatic dysfunction, renal dysfunction, allergy, and blood dyscrasias at baseline and excluding individuals with significant disturbances in their laboratory assessments or have a history of allergy to the components of the therapeutic agent or placebo (as defined by the exclusion criteria below). We will monitor complete blood count (CBC), liver function tests (LFT), venous blood gas (VBG or bicarbonate/CO2), electrolytes, and creatinine, and urinalysis with urine creatinine, calcium, and protein at baseline and regularly throughout the study, and if any individual meets exclusion criteria at any point during the study, we will terminate their treatment. Patients may develop acidosis on acetazolamide therapy, which may lead to inability to continue the therapy longer or a decrease in dosage. Acetazolamide has been associated with growth suppression in pediatric patients, although not all individuals have been reported to have poor growth and the dosages associated with growth suppression have not been consistent. Growth has been reported to resume and improve after discontinuation of acetazolamide. We will monitor growth parameters (height, weight, head circumference) regularly throughout the study and tailor their management and continuation in the study on a case by case basis. We will monitor patients' acid/base status and titrate acetazolamide accordingly. We will also obtain a one-time measurement of acetazolamide serum concentration at steady state at the six-month visit.

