## 8.5 Stopping Rules

Any SAEs greater than grade 3 (severe) as defined as "marked limitation in activity, medical intervention/therapy required, hospitalizations possible" will qualify as study stoppage for the rest of the study. The central Data and Safety Monitoring Board (DSMB) will be notified and they will determine if the study would need to be placed on hold with IRB. The study may be restarted if the SAE resolves or is deemed unrelated to the study.

Additionally, if clinical laboratory results show:

- Hepatic impairment defined as  $AST/ALT > 3.0 - 5.0 \times ULN$  if baseline was normal;  $> 3.0 - 5.0 \times \text{baseline}$  if baseline was abnormal
- Renal impairment defined as serum creatinine 1.5-1.9 times ULN for age OR  $\geq 26.5 \text{ umol/l}$  increase from ULN for age

If no other cause for these laboratory changes are likely, then drug will be stopped, and repeat labs will be obtained at reasonable intervals per investigator's clinical judgement after discontinuation until labs have normalized to stabilized. Treatment may be restarted if labs have returned to baseline using the same ramp up schedule as described for visit 2 and 3. The DSMB will also be notified.

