## 8.6 Medical Monitoring

It is the responsibility of the Investigator at each site to oversee the safety of the study at his/her site. Any SAE will be reported to the DSMB, which will make decisions regarding unblinding. This safety monitoring will include careful assessment and appropriate reporting of adverse events as noted above, as well as the construction and implementation of a site data and safety-monitoring plan (see section 10 "Study Monitoring, Auditing, and Inspecting"). Medical monitoring will include a regular assessment of the number and type of serious adverse events.

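### The SAE definition in section 8.1 is a closed list with no medical-judgement criterion, so a narrow class of related, medically important events misses prompt DSMB reporting and safety endpoint (b)

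*Combined protocol and SAP*

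**What the plan says.** The Serious Adverse Event paragraph of section 8.1 opens with "Serious problems/events can be well defined and include" and lists death, threat to life, hospitalisation, disability or incapacity, and birth defect. It ends: "All adverse events that do not meet any of the criteria for serious, should be regarded as" non-serious.

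Two neighbouring definitions in 8.1 are wider. Item (7) of the UPIRTSO seriousness criterion admits other problems or events "that in the opinion of the local investigator may adversely affect the rights, safety, or welfare of the subjects or others". The Adverse Event definition has similar judgement wording. Only the SAE definition has none.

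Section 1.5 states that "severe adverse reactions that have been reported with administration of acetazolamide include seizures, muscle paralysis, hepatic necrosis" and others, 15 in all.

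Several actions depend on the SAE label:
- Section 8.6: "Any SAE will be reported to the DSMB, which will make decisions regarding unblinding". Section 5.2 also sends SAEs to the DSMB.
- Section 8.2 requires immediate reporting of SAEs that are at least possibly related.
- Part (b) of the primary safety endpoint (3.6, analysed in 7.2) is the incidence of drug-related SAEs.
- The study-level rule in 8.5 begins "Any SAEs greater than grade 3 (severe".
- FDA reporting in 8.3.2 covers serious suspected reactions.

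**The concern.** Seriousness decides which events are escalated one by one. If the definition admits only five outcomes, an event that a clinician regards as important but that produces none of them has to be recorded as non-serious, whatever the investigator thinks. The DSMB then hears of it at a scheduled review and not when it happens, and it is left out of the count of related SAEs.

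This matters here because the drug's known reactions include seizures and blood dyscrasias, which can be found or treated without inpatient admission, and because titration and most laboratory checks are done remotely.

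**Working it through.** No sample size, power or rate is involved, so the check is textual. I took one test event and followed it through every route that depends on seriousness, and then through every route that does not.

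**Test event.** A drug-related seizure treated without inpatient admission, or a low cell count found on an outpatient CBC, judged neither life-threatening nor disabling. I assume that emergency treatment followed by discharge is not hospitalisation.

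**Step 1: classification.** None of the five outcomes applies. The word for inclusion in the opening sentence might suggest an open list, but the last sentence removes that latitude. The event is non-serious.

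**Step 2: does UPIRTSO catch it?** Its item (7) might, but UPIRTSO also requires the event to be unanticipated, and unanticipated events are "those that are not already described as potential risks in the protocol, consent document, not listed in the acetazolamide package insert". The section 1.5 reactions are described in the protocol and taken from the package insert, so they fall outside unless their frequency or severity is increased.

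**Step 3: routes that depend on seriousness.**

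| Route | Result for the test event |
|---|---|
| Event-level DSMB report (5.2, 8.6) | Missed |
| Immediate reporting of related SAEs (8.2) | Missed |
| Safety endpoint (b) (3.6, 7.2) | Missed; counted in (a) only |
| FDA 7- and 15-day case reports (8.3.2) | A listed reaction is normally expected and so excluded anyway; an unlisted event is missed if the 8.1 definition governs |
| FDA rate-increase clause (8.3.2) | Affected, because it counts serious reactions |
| Study stopping rule (8.5) | Little change on the literal wording (see objection) |

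**Step 4: routes that do not depend on seriousness.**
- The laboratory rules in 8.1 and 8.5 act whatever the SAE status, and 8.5 notifies the DSMB. They cover AST/ALT and creatinine only. No blood-count threshold is given, although 1.5 names agranulocytosis, aplastic anaemia, haemolytic anaemia and pancytopenia.
- Section 8.4 requires a report when a subject is unblinded for safety, SAE or not. The test event need not lead to unblinding.
- The 7.2 summaries keep the event: related events of grade 1 or higher by arm, maximum CTCAE grade by type, and discontinuations due to AEs.
- The DSMB reviews safety yearly (8.6.1). The blinded phase is 26 weeks, half of that interval (26/52). Depending on when the review falls, a subject could have the event, finish the blinded phase and begin open-label acetazolamide at Visit 5 before the DSMB sees it.

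**The case against.** The strongest reply is that the gap is narrow and that several consequences a reader might infer do not follow. Most of this stands.

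- **A reader might infer that any severe reaction managed without admission escapes.** It does not. Life-threatening and disabling events are SAEs without admission, which covers many of the 15 reactions. Five of the 15 are hepatic or renal, and they reach the DSMB under 8.5 if they meet its laboratory thresholds.
- **A reader might see a contradiction between severe in 1.5 and non-serious in 8.1.** Section 8.2 expressly separates the two terms.
- **A reader might infer that the stopping rule is bypassed.** Read literally, the rule needs a grade above 3. Grade 4 in Table 4 means risk of death, which is already an SAE criterion. The gap matters only if the rule is meant to include grade 3, whose description it quotes, or if the CTCAE-based criteria assign grade 4 without a judged risk of death. The modified criteria in Appendix D are not available to check.
- **A reader might infer that listed reactions are lost to FDA reporting.** Being expected already keeps them out of case reports. Section 8.3.2 also refers to the IND reporting requirements, so 8.1 is not shown to be the only gate.
- **A reader might want a number.** With 13 per arm, one event is 1/13 = 7.7%; with 17 on drug, if accrual reached 33, it is 1/17 = 5.9%. These figures restate the sample size and do not measure the defect.
- **A reader might propose one definition of serious throughout.** UPIRTSO covers financial and legal harm and breach of confidentiality. Merging the two would turn a confidentiality breach into an SAE sent to the DSMB for an unblinding decision.

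Section 8 also sends significant blood or urine changes to the principal investigator for re-evaluation. That is a safeguard, but it does not reach the DSMB. None of these replies supplies the missing criterion, or restores prompt DSMB notice or endpoint (b) for the test event.

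**Conclusion.** The point holds for a defined and narrow class: related, medically important events that are not admitted, not judged life-threatening, not disabling, and not caught by the AST/ALT or creatinine rules. For these, the written rule requires a non-serious label. The certain effects are loss of event-level DSMB notice, of immediate reporting under 8.2, and of a place in safety endpoint (b). The FDA effect is limited to unlisted events and the rate-increase clause. The stopping-rule effect is conditional on how 8.5 and the CTCAE-based grades are read. No event data are lost, because the AE summaries keep every event.

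How often this would happen cannot be derived, since section 1.5 gives no incidence. The conclusion assumes that sites apply the closing sentence of the SAE definition as written.

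**What to change.** Add one item to the SAE list in 8.1: *any other medically important event that, in the investigator's judgement, may jeopardise the subject or require intervention to prevent one of the outcomes above*. Give the section 1.5 severe reactions as examples, and update the seriousness field on the CRF.

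Keep the UPIRTSO definition separate, and state that its item (7) does not define SAE seriousness. The sponsor should also reconcile the threshold in 8.5 with the grade 3 description quoted beside it, so that it is clear which SAEs the rule covers.

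The cost is a short protocol amendment, one CRF change and a few more SAE reports. Each of these would go to the DSMB, which would then have to consider unblinding under 8.6. Sample size and the primary efficacy analysis are unaffected.

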### Adverse Event Reporting Period

The study site will document all AEs that occur (whether or not related to study drug) within one week of the investigator becoming aware of the event. The collection period for all AEs will begin after informed consent is obtained and end after procedures for the final study visit have

been completed. In accordance with the standard operating procedures and policies of the local Institutional Review Board (IRB), the site investigator will report SAEs to the IRB.

### **Pre-existing Condition**

A pre-existing condition is one that is present at the start of the study. A pre-existing condition should be recorded as an adverse event if the frequency, intensity, or the character of the condition worsens during the study period.

### **General Physical Examination Findings**

At screening, any clinically significant abnormality should be recorded as a pre-existing condition. At the end of the study, any new or worsening clinically significant findings/abnormalities that meet the definition of an adverse event must also be documented and reported as an adverse event.

### **Post-study Adverse Event**

All unresolved adverse events should be followed by the investigator until the events are resolved, the subject is lost to follow-up, or the adverse event is otherwise explained. At the last scheduled visit, the investigator should instruct each subject to report, to the investigator, any subsequent event(s) that the subject, or the subject's personal physician, believes might reasonably be related to participation in this study.

### **Abnormal Laboratory Values**

A clinical laboratory abnormality should be documented as an adverse event if they meet the following criteria:

- Hepatic impairment defined as AST/ALT  $>3.0 - 5.0 \times$  ULN if baseline was normal;  $>3.0 - 5.0 \times$  baseline if baseline was abnormal
- Renal impairment defined as serum creatinine 1.5-1.9 times ULN for age OR  $\geq 26.5 \text{ umol/l}$  increase from ULN for age

If these values are noted and no other cause for these laboratory changes are likely, then drug will be stopped, and repeat labs will be obtained at reasonable intervals per investigator's clinical judgement after discontinuation until labs have normalized to stabilized. Treatment may be restarted if labs have returned to baseline using the same ramp up schedule as described for visits 2, 3 and 4. These changes in treatment will be documented.

### **Hospitalization, Prolonged Hospitalization or Surgery**

Any adverse event that results in hospitalization or prolonged hospitalization should be documented and reported as a serious adverse event unless specifically instructed otherwise in this protocol. Any condition responsible for surgery should be documented as an adverse event if the condition meets the criteria for an adverse event.

Neither the condition, hospitalization, prolonged hospitalization, nor surgery are reported as an adverse event in the following circumstances:

- Hospitalization or prolonged hospitalization for diagnostic or elective surgical procedures for a preexisting condition. Surgery should **not** be reported as an outcome of an adverse

event if the purpose of the surgery was elective or diagnostic and the outcome was uneventful.

- Hospitalization or prolonged hospitalization required to allow efficacy measurement for the study.
- Hospitalization or prolonged hospitalization for therapy of the target disease of the study, unless it is a worsening or increase in frequency of hospital admissions as judged by the clinical investigator.

## 8.2 Recording of Adverse Events

At each contact with the subject, the study team must seek information on adverse events by specific questioning and, as appropriate, by examination. Information on all adverse events should be recorded immediately in the source document, and also in a separate adverse event worksheet. All clearly related signs, symptoms, and abnormal diagnostic, laboratory or procedure results should be recorded in the source document.

All adverse events occurring during the study period must be recorded. The clinical course of each event should be followed until resolution, stabilization, or until it has been ultimately determined that the study treatment or participation is not the probable cause. Serious adverse events that are still ongoing at the end of the study period must be followed up to determine the final outcome. Any serious adverse event that occurs during the Adverse Event Reporting Period and is considered to be at least possibly related to the study treatment or study participation should be recorded and reported immediately.

The most up to date National Cancer Institute's Common Terminology Criteria for Adverse Events (CTCAE) should be used to assess and grade AE severity, including laboratory abnormalities judged to be clinically significant. The modified criteria can be found in the study manual (appendix D). If the experience is not covered in the modified criteria, the guidelines shown in Table below should be used to grade severity. It should be pointed out that the term "severe" is a measure of intensity and that a severe AE is not necessarily serious.

**Table 4. AE Severity Grading**

Severity (Toxicity Grade)	Description
Mild (1)	Transient or mild discomfort; no limitation in activity; no medical intervention or therapy required. The subject may be aware of the sign or symptom but tolerates it reasonably well.
Moderate (2)	Mild to moderate limitation in activity, no or minimal medical intervention/therapy required.
Severe (3)	Marked limitation in activity, medical intervention/therapy required, hospitalizations possible.
Life-threatening (4)	The subject is at risk of death due to the adverse experience as it occurred. This does not refer to an experience that hypothetically might have caused death if it were more severe.

## AE Relationship to Study Drug

The relationship of an AE to the study drug should be assessed using the following the guidelines in Table .

**Table 5. AE Relationship to Study Drug**

Relationship to Drug	Comment
Definitely	Previously known toxicity of agent; or an event that follows a reasonable temporal sequence from administration of the drug; that follows a known or expected response pattern to the suspected drug; that is confirmed by stopping or reducing the dosage of the drug; and that is not explained by any other reasonable hypothesis.
Probably	An event that follows a reasonable temporal sequence from administration of the drug; that follows a known or expected response pattern to the suspected drug; that is confirmed by stopping or reducing the dosage of the drug; and that is unlikely to be explained by the known characteristics of the subject's clinical state or by other interventions.
Possibly	An event that follows a reasonable temporal sequence from administration of the drug; that follows a known or expected response pattern to that suspected drug; but that could readily have been produced by a number of other factors.
Unrelated	An event that can be determined with certainty to have no relationship to the study drug.

## 8.3 Reporting of Serious Adverse Events and Unanticipated Problems

When an adverse event has been identified, the study team will take appropriate action necessary to protect the study subject and then complete the Study Adverse Event Worksheet and log. The investigator will evaluate the event and determine the necessary follow-up and reporting required.

### 8.3.1 Investigator reporting: notifying the IRB

The investigator will report to the IRB any UPIRTSOs and NonUPIRTSOs according to the IRB Policy and Procedures.

Information collected on the adverse event worksheet:

- Subject's name:
- Medical record number:
- Disease/histology (if applicable):
- The date the adverse event occurred:
- Description of the adverse event:
- Relationship of the adverse event to the research (drug, procedure, or intervention):
- If the adverse event was expected:

- The severity of the adverse event: (use a table to define severity scale 1-5)
- If any intervention was necessary:
- Resolution: (was the incident resolved spontaneously, or after discontinuing treatment)
- Date of Resolution:

The investigator will review all adverse event reports to determine if specific reports need to be made to the IRB. The investigator will sign and date the adverse event report when it is reviewed. For this protocol, only directly related SAEs/UPIRTSOs will be reported to the IRB.

